3.8 Screen Failures

There is no screening period in Study 270 as only subjects completing Study 248 and directly rolling over to Study 270 are eligible for inclusion. However a subject who does not meet baseline inclusion/exclusion criteria for Study 270 may still be considered a screening failure, which is defined as a subject from whom informed consent is obtained and is documented in writing (ie, subject signs an ICF), but who is not started on Study 270 open-label treatment. Subjects who meet this criterion and are listed as screen failure subjects in Study 270 are not permitted to be re-screened at a later date.

Protocol 31-10-270

3.9 Definition of Completed Subjects

The treatment period is defined as the time period during which subjects are evaluated for primary and/or secondary objectives of the trial irrespective of whether or not the subject actually received all doses of the study medication. Subjects who are evaluated at the last scheduled visit during the treatment period will be defined as trial completers. Subjects who have their last visit by 31 Dec 2018, because they have reached the end of the study, will be defined as completers. For purposes of this trial, subjects who discontinue due to the commercial availability of study drug in the country where the study is being conducted will be defined as completers. In addition, subjects in countries where a managed access program is available for continued treatment with aripiprazole at the time of trial closure in their respective country, regardless of whether they transition to a managed access program, will also be defined as completers. Protocol-specified post-treatment follow-up contacts will not qualify as “last scheduled” visit.

3.10 Definition of Subjects Lost to Follow-up

Subjects who cannot be contacted at any time up through the last scheduled follow-up visit and who do not have a known reason for discontinuation (eg, withdrew consent or AE, etc) will be classified as “lost to follow-up” as the reason for discontinuation. Three attempts will be made by investigative sites to reach subjects, two by phone and one via certified mail.

3.11 Subject Compliance

Visit compliance is critical to achieving and maintaining stability of psychotic symptoms and to maintaining subjects on a schedule that will lead to completion of the IM Depot treatment within an acceptable time window. The key features of compliance can be summarized as follows:

- 1) IM depot injections are to be administered within an interval of 28 days between injections. The minimum allowable interval between IM depot injections is 26 days and the maximum interval is 38 days. Every effort should be made to adhere to the 28-day cycle.
- 2) If a subject misses 2 consecutive injections at any time in the study, or if a subject misses 3 injections in a 52-week time period, then this subject is considered noncompliant and must be withdrawn from the study.

Evaluations conducted outside of the windows defined in [Table 3.6-1](#) will be considered deviations, but will not impact the subject’s ability to continue the study.

Protocol 31-10-270

Visit windows are provided not only to allow flexibility with scheduling, but also to assure an adequate supply of study medication between injections. If a subject misses an injection, the injection should be given at the earliest opportunity. A missed dose of IM depot is defined as a lapse of > 38 days between injections. The minimum interval of 26 days and maximum interval of 38 days between injections is to ensure that therapeutic plasma concentrations of aripiprazole are maintained.

The time and date of each dose of aripiprazole IM Depot will be recorded on the CRF. If a dose was not administered as scheduled, an explanation will be provided in the CRF and supported by source documentation. The accountability of IM depot vials will be maintained at the vial level. Subjects who, in the investigator's judgment, are noncompliant with the IM depot injection schedule should be counseled on the importance of adhering to the treatment schedule. Reasons for noncompliance should be determined, if possible. Investigators should use their judgment to assess the feasibility of continuing subjects in the study who are significantly noncompliant.

3.12 Protocol Deviations

This trial is intended to be conducted as described in this protocol. In the event of a significant deviation from the protocol due to an emergency, accident, or mistake (eg, study drug dispensing or subject dosing error, treatment assignment error, subject enrolled in violation of significant eligibility criteria or concomitant medication criteria), the investigator or designee must contact the sponsor's designee (Medical Monitor) at the earliest possible time according to the Approval for Study Continuation process which is outlined in the Operations Manual. This will allow an early joint decision regarding the subject's continuation in the trial. This decision will be documented by the investigator and the designated Medical Monitor, and reviewed by the study monitor.

4 Restrictions

4.1 Prohibited Medications

Medications that are prohibited or restricted prior to screening and/or during the trial are listed by phase in [Table 4.1-1](#). No prohibited or restricted medications should be used within the visit windows when transitioning from Study 248 to Study 270. The prohibited and restricted medications also apply to any clinical transition period within allowed visit windows from Study 248 into Study 270.

Protocol 31-10-270

Table 4.1-1 List of Medications Prohibited or Restricted in Study 270	
Psychotropic Medications	
Antipsychotics	Not allowed
Antidepressants (including MAOIs)	Allowed, except for CYP2D6 or CYP3A4 inhibitors or CYP3A4 inducers
Benzodiazepine ^a	Allowed
Mood stabilizers	Allowed
Non-benzodiazepine sleep aids ^a	Allowed
Other Medications	
Anticholinergics	Allowed
Propranolol (for akathisia, tremor, or if taking for cardiac reasons) ^b	Allowed
Varenicline	Not allowed
Nutritional supplements and non-prescription herbal preparations with CNS effects (eg, St. John's Wort, omega-3 fatty acids, kava extracts, GABA supplements, etc.)	Allowed, but use caution
CYP3A4 or CYP2D6 inhibitors or CYP3A4 inducers (see Section 4.2.1)	Not allowed

CNS = central nervous system; GABA = gamma-aminobutyric acid.

Note: No prohibited or restricted medications should be used within the visit windows when transitioning from Study 248 to Study 270. The prohibited and restricted medications also apply to any clinical transition period within allowed visit windows from Study 248 into Study 270.

^aBenzodiazepine use is allowed during the study to manage treatment emergent AEs such as agitation, anxiety, and insomnia; however, non-benzodiazepine sleep aids are recommended for insomnia. Combined use of both drug classes (ie, benzodiazepines and non-benzodiazepine sleep aids) as treatment for insomnia is not allowed. Benzodiazepine use should be discontinued as soon as the AE for which it was initiated subsides, as per the investigator's discretion to avoid any withdrawal effects.

^bSubjects receiving propranolol for heart disease may remain on stable, pre-trial doses, as needed, throughout the study so long as the total dose does not exceed 60 mg/day.

4.2 Other Restrictions

4.2.1 Restricted Therapies and Precautions

No prohibited or restricted medications should be used within the visit windows when transitioning from Study 248 to Study 270. The prohibited and restricted medications also apply to any clinical transition period within allowed visit windows from Study 248 into Study 270.

The subject's best medical interests should guide the investigator in the management of conditions that are pre-existing or that develop during the study (intercurrent illness or AEs). All study personnel should be familiar with the content of the Investigator's Brochure for aripiprazole⁹ in order to manage the subject's condition adequately and select appropriate concomitant medications, if needed. The investigator should carefully

Protocol 31-10-270

assess the potential for interaction with aripiprazole before prescribing any concomitant medications.

The use of CYP3A4 or CYP2D6 inhibitors and CYP3A4 inducers is not permitted during the study, as they may affect the pharmacokinetics of aripiprazole. Examples of inhibitors include, but are not limited to, amiodarone, celecoxib, chlorpheniramine, cimetidine, clarithromycin, clemastine, diltiazem, erythromycin, itraconazole, ketoconazole, methadone, nafazodone, pyrilamine, quinidine, rifampin, terbinafine, tripeleminamine, verapamil, and human immunodeficiency virus protease inhibitors (eg, amprenavir, indinavir, nelfinavir, ritonavir, and saquinavir). Examples of inducers include, but are not limited to, carbamazepine, dexamethasone, phenobarbital, phenytoin, and non-nucleoside reverse transcriptase inhibitors (eg, efavirenz and nevirapine). The Medical Monitor should be consulted for any questions regarding the potential for pharmacokinetic interactions with concomitant medications used by subjects during the trial.

Other guidelines for use of concomitant medications during the trial include:

- Treatment of allergy symptoms: Non-sedating antihistamines are permitted.
- Treatment of cold/flu symptoms: Medications containing ingredients that have central nervous system (CNS) effects should be limited to short-term use and discontinued as soon as the symptom(s) resolve.
- Treatment of gastroesophageal reflux disease (GERD): The use of cimetidine is prohibited. All other medications for the treatment of GERD are permitted.
- Treatment of hypertension: Medications that are CYP3A4 or CYP2D6 inducers or inhibitors (eg, verapamil) are prohibited.
- Treatment of diabetes: No additional guidelines.
- Treatment of infection: No additional guidelines.

4.2.2 Non-therapy Precautions and Restrictions

Subjects will be instructed to refrain from drinking alcoholic beverages or using illicit drugs during participation in the trial. The investigator should consult with the Medical Monitor in the event that a false-positive drug screen result is suspected (eg, drug screen testing in subjects taking medications that have phenylpropanolamine or pseudoephedrine may produce a false-positive result for amphetamine). The investigator may request a blood or urine drug screen at any time during the study if there is a suspicion of illicit drug use.

Protocol 31-10-270

5 Reporting of Adverse Events

The following describes the methods and timing for assessing, recording, and analyzing safety parameters, as well as the procedures for eliciting reports of and recording and reporting AEs and intercurrent illnesses and the type and duration of the follow-up of subjects after AEs.

5.1 Definitions

An adverse event (AE) is defined as any new medical problem, or exacerbation of an existing problem, experienced by a subject while enrolled in the study, whether or not it is considered drug-related by the investigator.

A serious AE (SAE) includes any event that results in any of the following outcomes:

- Death.
- Life-threatening, ie, the subject was, in the opinion of the investigator, at immediate risk of death from the event as it occurred. It does not include an event that, had it occurred in a more severe form, might have caused death.
- Persistent or significant disability/incapacity.
- Requires in-patient hospitalization or prolongs hospitalization.
- Congenital anomaly/birth defect.
- Other medically significant events that, based upon appropriate medical judgment, may jeopardize the subject and may require medical or surgical intervention to prevent one of the outcomes listed above, eg, allergic bronchospasm requiring intensive treatment in an emergency room or home, blood dyscrasias or convulsions that do not result in hospitalization, or the development of drug dependency or drug abuse.

Non-serious adverse events are all AEs that do not meet the criteria for a "serious" adverse event.

Immediately Reportable Event (IRE):

- Any serious adverse event.
- Any AE that necessitates discontinuation of study drug.
- Potential Hy's Law cases (Any increase of AST or ALT \geq three times the upper normal limit with \geq two times increase in total bilirubin).
- Pregnancies are also defined as IREs. Although normal pregnancy is not an adverse event, it will mandate drug discontinuation and must be reported on an IRE form to Otsuka Pharmaceutical Development and Commercialization, Inc. (OPDC). Pregnancy will only be documented on the AE-CRF if there is an abnormality or complication.

Protocol 31-10-270

Clinical Laboratory Changes: It is the investigator's responsibility to review the results of all laboratory tests as they become available. This review will be documented by the investigator's dated signature on the laboratory report. For each abnormal laboratory test result, the investigator needs to ascertain if this is an abnormal (ie, clinically significant) change from baseline for that individual subject. (This determination, however, does not necessarily need to be made the first time an abnormal value is observed. The investigator may repeat the laboratory test or request additional tests to verify the results of the original laboratory tests). If this laboratory value is determined by the investigator to be an abnormal change from baseline for that subject, this is considered an AE.

Severity: AEs will be graded on a 3-point scale and reported as indicated on the CRF.

The intensity of an adverse experience is defined as follows:

- 1 = Mild:** Discomfort noticed, but no disruption to daily activity.
- 2 = Moderate:** Discomfort sufficient to reduce or affect normal daily activity.
- 3 = Severe:** Inability to work or perform normal daily activity.

The causal relationship of the study drug to an AE is assessed as related or unrelated, as follows:

Related:

Definite: There is a reasonable causal relationship between the study drug and the AE or the event responds to withdrawal of the study drug (dechallenge) and the Investigator's assessment of the event is deemed "Definitely Related" based on the sum of available clinical information gathered.

Probable: There is a reasonable causal relationship between the study drug and the AE. The event may respond to dechallenge or the Investigator's assessment of the event is deemed "Probably Related" based on the sum of available clinical information gathered.

Possible: There is a reasonable causal relationship between the study drug and the AE. Dechallenge is lacking or unclear and the Investigator's assessment of the event is deemed "Possibly Related" based on the sum of clinical information gathered.

Protocol 31-10-270

Unrelated:

Not Likely: There is a temporal relationship to study drug administration, but based on the available clinical information the Investigator deems that there is no reasonable causal relationship between the study drug and the event.

Not Related: Based on the available clinical information the Investigator deems that there is no temporal or causal relationship to study drug administration.

5.2 Eliciting and Reporting Adverse Events

The investigator will periodically assess subjects for the occurrence of AEs. In order to avoid bias in eliciting AEs, subjects should be asked the following nonleading question: "How have you felt since your last visit?" All AEs (serious and nonserious) reported by the subject must be recorded on the source documents and CRFs provided by the sponsor or designee.

Note: Normal pregnancy is not an AE and should not be recorded on the AE form of the CRF; guidelines outlined in [Section 5.4](#) should be followed for pregnancy reporting.

In addition, OPDC or their designee (see [Appendix 2](#)) must be notified immediately by telephone or fax of any immediately reportable events according to the procedure outlined below ([Section 5.3](#)). Special attention should be paid to recording hospitalization and concomitant medications.

5.3 Immediately Reportable Events

The investigator must report any SAE, potential Hy's law case or confirmed pregnancy, by telephone [[contact]] or by fax [[contact]] to OPDC or their designee immediately after the investigator becomes aware of the event. An Immediately Reportable Event (IRE) form should be completed and sent by fax or overnight courier to the sponsor or their designee up to and including 24 hours of knowledge of the event by the site. (Please note that the IRE form is NOT the adverse event case report form.)

Non-serious events that require discontinuation of study drug (including laboratory abnormalities) should be reported to OPDC or their designee up to and including 3 working days. The IRE form should be completed and sent by fax or overnight courier to OPDC or their designee.

Subjects experiencing serious adverse events should be followed clinically until their health has returned to baseline status or until all parameters have returned to normal, or have otherwise been explained. It is expected that the investigator will provide or arrange appropriate supportive care for the subject.

Protocol 31-10-270

5.4 Pregnancy

WOCBP is defined as ALL women unless they have had an oophorectomy and/or hysterectomy or have been menopausal for at least 12 consecutive months. This should be documented in their medical history. Subjects with positive serum test results will be excluded from the study.

WOCBP who are sexually active must use an effective method of birth control during the course of the trial so risk of failure is minimized. Unless the subject and his/her partner(s) are sterile (ie, women who have had an oophorectomy and/or hysterectomy or have been postmenopausal for at least 12 consecutive months; or men who have had orchidectomy) or remain abstinent, two of the following precautions must be used: vasectomy, tubal ligation, vaginal diaphragm, IUD, birth control pills, birth control implant, condom with spermicide, or sponge with spermicide. Any single method of birth control, including vasectomy and tubal ligation, may fail, leading to pregnancy.

Before enrolling WOCBP in this clinical trial, investigators must review guidelines about trial participation for WOCBP. The topics should include:

- General information
- Informed Consent Form
- Pregnancy prevention information
- Drug interactions with hormonal contraceptives
- Contraceptives in current use
- Guidelines for the follow-up of a reported pregnancy

Prior to trial enrollment, WOCBP must be advised of the importance of avoiding pregnancy during trial participation and the potential risk factors for an unintentional pregnancy. Males should also be instructed not to impregnate their partners while on study drug. The subject must sign an ICF stating that the above-mentioned risk factors and the consequences were discussed.

During the trial, all WOCBP should be instructed to contact the investigator immediately if they suspect they might be pregnant (eg, missed or late menstrual cycle).

If a subject or investigator suspects that the subject may be pregnant prior to administration of the study drug, administration must be withheld until the results of blood serum pregnancy tests are available. If the pregnancy is confirmed, the subject must not receive the study drug or be enrolled in the trial. If pregnancy is suspected while the subject is receiving treatment, the study drug must be withheld immediately

Protocol 31-10-270

(if reasonable, taking into consideration any potential withdrawal risks) until the result of the pregnancy test is known. If pregnancy is confirmed, the study drug will be permanently discontinued in an appropriate manner (eg, dose tapering if necessary for subject safety) and the subject will be withdrawn from the trial. [Exceptions to trial discontinuation may be considered for life-threatening conditions only after consultations with Drug Safety Services (see [Appendix 2](#)).]

The investigator must immediately notify Drug Safety Services of any pregnancy associated with exposure to aripiprazole IM Depot. For subjects who received at least one dose of IM depot, the reporting period includes 150 days after last injection for female subjects and 180 days after the last injection for female partners of male subjects. For all pregnancy reports, the investigator will record the event on the IRE form and forward it to the Drug Safety Services department of the sponsor's designee. Drug Safety Services will forward Pregnancy Surveillance Form(s) for monitoring the outcome of the pregnancy. Pregnancy will only be documented on the AE CRF if there is an abnormality or complication to be reported.

Protocol-required procedures for trial discontinuation and follow-up must be performed on the subject unless contraindicated by pregnancy (eg, x-ray studies). Other appropriate pregnancy follow-up procedures should be considered if indicated. In addition, the investigator must report to the sponsor (or sponsor's designee) on appropriate Pregnancy Surveillance form(s), follow-up information regarding the course of the pregnancy, including perinatal and neonatal outcome. Infants will be followed for a minimum of 6 months.

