3.4.3 Exclusion Criteria

Subjects will be excluded if they meet any of the following exclusion criteria:

Table 3.4.3-1 Exclusion Criteria	
Sex and Reproductive Status	
1.	Sexually active males who are not practicing double-barrier birth control or who will not remain abstinent during the study and for 180 days following the last dose of study medication, or sexually active females of childbearing potential who are not practicing double-barrier birth control or who will not remain abstinent during the study and for 150 days following the last dose of study medication. If employing birth control, two of the following precautions must be used: vasectomy, tubal ligation, vaginal diaphragm, intrauterine device (IUD), birth control pill, birth control implant, condom with spermicide, or sponge with spermicide.
2.	Females who have a positive serum pregnancy test result at study entry.

Protocol 31-10-270

Table 3.4.3-1 Exclusion Criteria	
Target Disease	
3.	Subjects with a current DSM-IV-TR diagnosis other than schizophrenia, including schizoaffective disorder, MDD, bipolar disorder, delirium, dementia, amnesic or other cognitive disorders. Also, subjects with borderline, paranoid, histrionic, schizotypal, schizoid, or antisocial personality disorder.
Medical History and Concurrent Disease	
4.	Subjects with a significant risk of violent behavior or a significant risk of committing suicide based on the investigator's judgment.
5.	Subjects who currently meet DSM-IV-TR criteria for substance dependence; including alcohol and benzodiazepines, but excluding caffeine and nicotine.
6.	Subjects who have a history or evidence of a medical condition that would expose them to an undue risk of a significant AE or interfere with assessments of safety or efficacy during the course of the trial, including but not limited to hepatic, renal, respiratory, cardiovascular, endocrine, neurologic, hematologic, or immunologic disease as determined by the clinical judgment of the investigator.
7.	Subjects with epilepsy or a history of seizures, except for a single childhood febrile seizure, post traumatic, alcohol withdrawal, etc.
Physical and Laboratory Test Findings	
8.	Any subject with a positive drug screen for cocaine or other drugs of abuse (excluding marijuana, stimulants, and other prescribed medications).

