^h A urine pregnancy test is required for all WOCBP at baseline, every 3 months, and at Study Completion or the Early Termination visit, but can be performed at any point during the trial if pregnancy is suspected. All positive urine pregnancy test results must be confirmed by a serum test. WOCBP is defined as ALL women unless they have had an oophorectomy and/or hysterectomy or have been menopausal for at least 12 consecutive months. This should be documented in their medical history. Subjects with positive serum test results will be excluded from the study. Treated subjects with a positive serum pregnancy test must discontinue treatment, be withdrawn from the study, and an immediately reportable event (IRE) form should be completed.

ⁱ Urine drug screen and blood alcohol test are required at baseline and anytime at the investigator's discretion.

^j Aripiprazole IM Depot (400 mg or 300 mg) will be injected every month (study months are every 4 weeks which is defined as 28 [-2/+10] days).

Protocol 31-10-270

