3.6.1.6 Study Completion or Early Termination Visit

A Study Completion visit or Early Termination visit (-2/+10 days) will be performed and will include the following assessments: C-SSRS, AEs, concomitant medications, a urine pregnancy test for WOCBP, CGI-S, vital signs, and EPS assessments (AIMS, BARS, SAS), clinical laboratory tests, and body height and weight.

3.6.1.7 30-Day Post Treatment Follow-up Phone Call

A 30-Day Post Treatment Follow-up phone call will be performed 30 days (\pm 3 days) after it has been determined that the subject will no longer participate in this study and will include the recording of AEs that have occurred since the last visit and any concomitant medications taken since the last visit.

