3.6.4 End of Trial

The End of Trial Date is defined as the last Date of Contact or the Date of Final Contact Attempt from the Post-treatment Follow-up case report form (CRF) page for the last subject completing or withdrawing from the trial.

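### Pregnancies are reportable to 150 or 180 days after the last injection, but after the final-visit urine test no scheduled contact asks about pregnancy, so reporting depends on volunteered information

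*Protocol*

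**What the plan says.** **The reporting period.** Protocol section 5.4 says "the reporting period includes 150 days after last injection for female subjects and 180 days after the last injection for female partners of male subjects". Exclusion criterion 1 (Table 3.4.3-1) attaches the same lengths to contraception: men "during the study and for 180 days following the last dose of study medication", women "for 150 days following the last dose of study medication". Sections 5.1 and 5.3 make pregnancy an immediately reportable event, and 5.4 requires outcome surveillance, with infants followed for at least 6 months.

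**What is scheduled.** Table 3.6-1, footnote h: "A urine pregnancy test is required for all WOCBP at baseline, every 3 months, and at Study Completion or the Early Termination visit". A test may also be done whenever pregnancy is suspected. The only later contact is the 30-day phone call, which under 3.6.1.7 "will include the recording of AEs that have occurred since the last visit and any concomitant medications taken since the last visit". Section 5.5.1 describes the call in terms of ongoing AEs, new AEs and new serious AEs (SAEs). Section 5.2 adds: "Normal pregnancy is not an AE and should not be recorded on the AE form of the CRF".

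**What subjects are told.** Section 5.4: "During the trial, all WOCBP should be instructed to contact the investigator immediately if they suspect they might be pregnant". Its advice to men is to avoid causing a pregnancy during the time on drug.

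**Closure.** Under 3.6.4 the End of Trial date is the "last Date of Contact or the Date of Final Contact Attempt from the Post-treatment Follow-up case report form" page for the last subject.

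**The concern.** The protocol sets a long period after the last dose in which a pregnancy matters, but the means of learning of one largely stop at the final visit. The call asks about a category that excludes normal pregnancy. The instruction to make contact is limited to WOCBP and to the time of the trial. Partners of male subjects have the longest reporting period and no scheduled enquiry at any visit or call.

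What is at stake is safety case-finding. Collecting long-term safety data is the trial's secondary objective. A pregnancy that never reaches the investigator does not enter the surveillance and infant follow-up that 5.4 sets up.

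**Working it through.** **1. Check the plan's own figures.** The 150 and 180 days are stated rules with nothing to derive. Section 5.4 (reporting) and exclusion criterion 1 (contraception) agree on both.

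**2. List every enquiry after the last injection.**
- Final visit: urine test, WOCBP only.
- 30-day call: AEs and concomitant medications (3.6.1.7, Table 3.6-1); AEs and SAEs (5.5.1).
- After the call: nothing scheduled. The description of the current design in SAP section 3 shows the same single call.
- Partners of male subjects: no test or question at any point, so 0 of 180 days has a scheduled enquiry.

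**3. Size the period after the last test.** Let *v* be the days from the last injection to the final visit, and *P* = 150 or 180. The time left after the last test is *P* − *v*. The documents do not give *v*, so it is assumed:
- 26 to 38 days: one injection interval (section 3.11).
- 42 days: the approximate 6-week limit when the product becomes commercially available (section 3.1).
- 76 days = 2 × 38: withdrawal after two missed injections, each being a lapse of more than 38 days (section 3.11).

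**4. Size what would remain if the call did ask about pregnancy.** The time left is *P* − (*v* + *k*), with *k* = 27 to 33 days, counting the call from the last visit as 5.5.1 does.

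| *v* | After last test, of 150 | After call, of 150 | After call, of 180 |
|---|---|---|---|
| 26 | 124 (82.7%) | 91 to 97 (60.7% to 64.7%) | 121 to 127 (67.2% to 70.6%) |
| 28 | 122 (81.3%) | 89 to 95 (59.3% to 63.3%) | 119 to 125 (66.1% to 69.4%) |
| 38 | 112 (74.7%) | 79 to 85 (52.7% to 56.7%) | 109 to 115 (60.6% to 63.9%) |
| 42 | 108 (72.0%) | 75 to 81 (50.0% to 54.0%) | 105 to 111 (58.3% to 61.7%) |
| 76 | 74 (49.3%) | 41 to 47 (27.3% to 31.3%) | 71 to 77 (39.4% to 42.8%) |

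For example, *v* = 42 gives 150 − 42 = 108 days after the test, and 150 − (42 + 33) = 75 days after the latest call.

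**5. Passages that do not line up.**
- The call is timed from the decision that the subject will no longer take part (3.6.1.7; Table 3.6-1, footnote c) but from the last study visit in 5.5.1. If the decision comes before the final visit, the call falls earlier and the time after it is longer than in the table.
- Section 5.4 ties WOCBP contraception to the duration of the trial, and its advice to men to the time on drug. Exclusion criterion 1 and the reporting periods run to 150 and 180 days after the last dose.

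**The case against.** The strongest reply is that 5.4 sets a reporting duty and does not promise active surveillance. Section 5.3 starts the clock when the investigator becomes aware, and nothing ends the duty at the End of Trial date. SAEs are handled similarly in 5.5.2: active monitoring to 30 days, then reliance on what former subjects report. This stands. A reader might infer that the period is wholly unmonitored, that the reporting commitment fails, or that closing the trial cuts it off. The documents support none of these. Passive reporting remains, and the End of Trial date is administrative.

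A reader might also infer that the call cannot bring a pregnancy to light. That goes too far. Section 5.2 prescribes an open question about how the subject has felt, and its rule on normal pregnancy concerns where the event is recorded. Complications go on the AE form, a congenital anomaly is an SAE, and SAEs judged drug-related stay reportable after the last contact. The gap is mainly uncomplicated pregnancy.

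Nor can it be said that men are never told to report. The consent pages, Operations Manual and follow-up case report form (CRF) page were not available; only the protocol body can be said to lack the instruction.

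Finally, pregnancy is not an endpoint in protocol sections 3.5, 7.3 or 7.4, and the SAP's Appendix 4 lists only urine test results (LAB-6). No planned estimate is biased.

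What survives is narrower. No listed item on the last contact asks about pregnancy, and the self-report instruction in the protocol body covers neither the time after the trial nor partners.

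**Conclusion.** The point holds as a gap in ascertainment. After the final visit, learning of a pregnancy depends on someone volunteering it, so uncomplicated pregnancies may be under-ascertained. The direction is clear, but the number missed cannot be computed from the documents.

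For female subjects, about three-quarters of the reporting period follows the last test under ordinary final-visit timings (72% to 83%), and about half after late withdrawal. So it is not true of every subject that most of the period lies after the test. These shares rest on the assumed day of the final visit. For partners the absence of scheduled enquiry is complete and needs no assumption.

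A reader might infer that a further call at day 150 or 180 is needed. The documents do not make that case. Some subjects leave because the product is commercially available, or may continue through managed access (sections 3.1 and 3.9). Those who continue the drug are still exposed at that point, so the call could not isolate exposure from the trial.

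**What to change.** 1. Add a pregnancy question (the subject, or the partner of a male subject) to the existing 30-day call and its CRF page, and state it in 3.6.1.7, 5.5.1 and Table 3.6-1.
2. In 5.4, extend the instruction to report a suspected or confirmed pregnancy to the existing 150- and 180-day reporting periods, include male subjects for partner pregnancies, and give the instruction at the final visit. This is needed as well as the question, because with a final visit on day 26 to 42 at least half of each reporting period comes after the call.
3. Reconcile the time limits in 5.4's contraception and male-subject advice with exclusion criterion 1 and the reporting periods. Reconcile the two starting points for the call.

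The cost is one CRF field and minor wording. No visit or contact is added, and the End of Trial definition does not change.
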